## 2.2 Objective

The goal of the proposed study is to determine if temporary androgen suppression improves the clinical outcomes of Veterans who are hospitalized to an acute care ward due to COVID-19 as defined by an influenza severity scale or time to discharge.

## 2.3 Study Design

This study is a parallel, double-blind, placebo controlled, superiority trial in which participants will be randomized to the degarelix + BSC treatment group or to the placebo + BSC control group. The study will randomize 198 Veterans at four VA Medical Centers at a 2:1 treatment assignment ratio, i.e. 132 participants in the degarelix group and 66 participants in the placebo group. The total recruitment period will be approximately 90 days with an approximately follow-up period of 60 days. The

duration of the study will be approximately five months. Informed consent for the study will be obtained prior to participants' enrollment eligibility screening. Randomization will be performed via an Interactive Web Response System (IWRS), a computerized system that will allow authorized study personnel to randomize patients and obtain study treatment assignments using a stratified random block method once a participant has eligible to the study. Study drug treatment will be given according to the randomization assignment within 48 hours after randomization. BSC consists of supplemental oxygen, antibiotics, vasopressor support, peritoneal or hemodialysis, antibiotics, intravenous fluids, etc. The participants will be followed up till their discharge. The study flow is shown in Appendix 5.2. Both the participants and the treating physicians/nurses as well site investigators/coordinators will be blinded of the treatment assignment.

Participants will be followed until death or discharge, whichever comes first. If a patient dies or refuses to continue participation, he will be terminated. A termination form will be used to record the termination information for these patients. If a patient remains hospitalized beyond day 30, the patient will continue to be followed for clinical endpoints, but no additional research labs will be obtained.

Study treatment drug, degarelix (as the acetate) is formulated as a sterile lyophilized powder for injection. Degarelix forms a depot upon subcutaneous administration, from which it is released to the circulation. The long half-life after subcutaneous administration is a consequence of a very slow release of degarelix from the depot formed at the injection site(s). The 240 mg dosage is achieved by the administration of two 120 mg SQ doses in the deep abdominal subcutaneous tissue. Participants will be randomly assigned to receive a one-time dose of degarelix 240 mg SQ or matching placebo on randomization day (day 1). The matching placebo will contain equal volume 0.9% saline by following the 60 minute rule after the drug reconstitution. No dose modifications are allowed for degarelix.

Scheduled follow up forms will be filled out weekly after randomization upon till discharge after the randomization and Unscheduled follow-up form will be filled out on the time whenever the event occurs during the follow-up time (see Appendix 5.3.1 ).

## 2.4 Study Outcome Variables

### 2.4.1 Primary Outcome Variable

The primary outcome is defined as a composite endpoint of mortality, ongoing need for hospitalization, or requirement for mechanical ventilation/extracorporeal membrane oxygenation (ECMO) at 15 days after the randomization.

### 2.4.2 Secondary Outcome Variables

There are five secondary outcome measures

1. The composite endpoint of mortality, ongoing need for hospitalization, or requirement for mechanical ventilation/extracorporeal membrane oxygenation (ECMO) at 30 days after the randomization.
2. The time to clinical improvement as defined by a decline of 2 categories or more from the baseline on the modified 7-category ordinal scale of clinical status of hospitalized influenza patients (influenza scale, see Appendix 5.1) or hospital discharge, whichever comes first.
3. Inpatient mortality
4. Length of hospital stay
5. Duration of intubation for mechanical ventilation
6. Time to normal temperature (< 37.5°C for ≥ 48 hours)
7. The maximum severity of COVID-19 illness based on the influenza severity scale (see Appendix 5.1)

### 2.4.3 Exploratory Outcome Variables

*Prognostic factors associated with clinical outcomes*

Clinical Factors: Age, use of angiotensin converting enzyme inhibitors, the duration of pre-hospitalization symptoms, or the presence or absence of hypertension, cardiovascular disease, asthma, diabetes mellitus, or COPD

Laboratory Factors D-dimer, IL-6, LDH, ferritin, total WBC, absolute neutrophil count (ANC), absolute lymphocyte count (ALC), or testosterone

*Treatment effect on viral load and cytokines (GLA site only)*

Viral load NP epithelial cells, PBMC

Serum cytokines TNF- $\alpha$ , IL-1 $\beta$ , IL-6

Other TMPRSS2 expression, anti-viral Ab, genomic factors

#### **2.4.4 Safety Outcome Variables**

Safety measures include study-related adverse events (AE) and serious adverse events (SAE), and AE with special interest in the drug toxicity.

### **2.5 Study Assessments Used in the Analysis**

#### **2.5.1. Baseline Assessment**

Participants' demographics, medical history, vital signs, and concomitant medication use are collected at the baseline time point. Other baseline assessments will be collected the time between identification of an eligible participant and the randomization including medical history, laboratory measurements of D-dimer, IL-6, LDH, ferritin, total WBC, ANC, ALC, testosterone, and participant clinical status. Data collected during this period is used primarily for the participants' baseline characteristics used for the statistical analysis, monitoring recruitment, and randomization status. We will maintain the information of all identified potential participants. This will be accomplished by completing the screening form for every participant presenting to the clinical site for eligible operations including those who are excluded from the study for any reason.

#### **2.5.2. Follow-up Assessment**

Follow-up assessments will be collected after participants' randomization and treatment at day 1, 8, 15, 22, 30, and 60 for the scheduled follow-up assessments of concomitant medications, medical status, laboratory measurements, and clinical assessment. The follow-up assessments also include those unscheduled protocol deviations, AEs and SAEs, and participants' disposition status. The data collection schedule as shown in Appendix 5.3.2.

#### **2.5.3. Safety Assessment**

Timely and complete reporting of safety information assists study management in identifying any untoward medical occurrence. This contributes to patient safety,

regulatory compliance and improvements in study design or procedures. In addition, close attention to AEs provides valuable information about the safety and tolerability of study drugs. This study specific safety plan is designed to collect information on the safety and tolerability of the study medications; thus, reporting will be conducted in accordance with the requirements of GCP and other regulatory requirements governing clinical research in the US. In HITCH, patients will receive a regimen of FDA approved commercially available degarelix for injection (Firmagon®) 240 mg for subcutaneous use or matching placebo. Local Study Investigators, with assistance from their local SC, are responsible for collecting AE and SAE information regarding the patients at their sites. Non-serious AEs and SAEs will be collected from the time of randomization until 30 days after the last dose of study medication. Throughout the specified duration of AE and SAE collection, data will be collected through spontaneous local SC/LSI/Co-I contact, during in-person study visits, and gathered during telephone contacts and medical record reviews when performed (see Table of Scheduled Events). AEs will be collected based on a review of the electronic medical record. Adverse events that are open will require follow-up reports (if necessary) every 30 days until resolved or until the end of the trial. Adverse events reported to study staff and deemed related to the study drug(s) and all SAEs will be recorded on an AE or SAE form (respectively) and documented in source records (e.g., the electronic VA medical record and/or the patient's study record).

Severity of an Adverse Event The following categories are used to convey the severity of an adverse event:

- Grade 1 Mild; – Events require minimal or no treatment and do not interfere with the patient's daily activities
- Grade 2 Moderate; – Events result in a low level of inconvenience or concern with the therapeutic measures. Interferes with normal daily activities to some extent
- Grade 3 Severe; – Events interrupt a patient's usual daily activity and may require systemic drug therapy or other treatment. May severely interfere with or prevent normal daily activities
- Grade 4 Life-threatening consequences; – Events requiring urgent intervention

- Grade 5 Death related to AE.

Serious Adverse Event (SAEs) An AE is considered an SAE if, in the view of either the investigator or sponsor, it results in any of the following outcomes:

- Death
- A life-threatening AE
- Inpatient hospitalization or prolongation of existing hospitalization
- A persistent, significant, or permanent incapacity or substantial disruption in the patient's body function/structure, physical activities and/or quality of life
  - Congenital anomaly/birth defect; or
  - Important medical events that may not be immediately life-threatening, result in death, or require hospitalization may be considered serious when, based upon appropriate medical judgment, they may jeopardize the patient and may require medical or surgical intervention to prevent one of the outcomes listed in this definition. Such events include intensive treatment in an emergency room or at home for allergic bronchospasm; blood dyscrasias or convulsions that do not result in hospitalization; or development of drug dependency or drug abuse

Relatedness Relatedness involves an assessment of the degree of causality (attributability) between the study intervention and the event.

- Definitely Related: The event is clearly related to the study intervention – i.e. an event that follows a reasonable temporal sequence from administration of the study intervention follows a known or expected response pattern to the suspected intervention that is confirmed by improvement on stopping and reappearance of the event on repeated exposure and that could not be reasonably explained by the known characteristics of the patient's clinical state.
- Possibly Related: An event that follows a reasonable temporal sequence from administration of the study intervention follows a known or expected response pattern to the suspected intervention, but that could readily have been produced by a number of other factors.
- Not Related: The event is clearly not related to the investigational agent/procedure. - i.e. another cause of the event is most plausible; and/or a clinically

plausible temporal sequence is inconsistent with the onset of the event and the study intervention and/or a causal relationship is considered biologically implausible.

Unanticipated Adverse Event An AE that is new or greater than previously known, in terms of nature, severity, or frequency of occurrence, or any other unanticipated serious problem associated with the investigation that relates to the rights, safety, or welfare of participants, as documented in the protocol or other materials approved by the IRB of record or the characteristics of the study population.

Adverse Events of Special Interest Cardiac arrhythmias and thromboembolic events will be considered AEs of special interest. Any cardiac arrhythmia or thromboembolic event of grade 3-5 according to Common Terminology Criteria for Adverse Events version 5.0 (CTCAE v5.0; see Appendix 5.4) will be reported in a manner similar to SAEs, whereby the event will be reported to the HITCH reporting system within 3 calendar days of the Study Site Personnel becoming aware of the event.

All adverse events that are related to the study intervention or procedures are recorded at each research assessment visit (description, severity, relationship to study intervention, date onset, date resolution).

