placebo group). Based on an assumed 5% attrition rate, 198 patients will be required (i.e. 132 in the degarelix group and 66 in the placebo group) to achieve actual statistical significance at alpha level of 0.05 and power of 90%.

Study Schematic

Study Treatments

Patients assigned to the degarelix arm will receive degarelix 240 mg subcutaneously (SQ) in the periumbilical area. The degarelix or matched placebo will be administered within 24 hours of randomization (i.e. within 24 hours of Day 1). Patient in the BSC alone arm will receive placebo. Patients, investigators, and treating physicians will be blinded to treatment assignment (i.e. double blinding).

Screening

Male Veterans who have been hospitalized or are in the process of being admitted to an acute care ward from the outpatient setting or emergency department (ED) and have a positive nasopharyngeal swab for SARS-CoV-2 based on an approved RT-PCR assay will be screened. Patients will complete screening within 72 hours of signing the informed consent form (ICF).

Eligibility Criteria

Inclusion Criteria

1. Male Veterans admitted to a VA hospital.
2. Age ≥ 18
3. Hospitalized on an acute care ward with a diagnosis of COVID-19 contributing to hospitalization.
4. Positive RT-PCR assay for SARS-CoV-2 on a nasopharyngeal swab sample.
5. Severity of COVID-19 illness of level 3, 4 or 5 on the influenza severity scale (see Appendix A) at the time of randomization.

6. The subject (or legally acceptable representative if applicable) must provide informed consent for the trial.

Exclusion Criteria

1. History of severe hypersensitivity to degarelix or any component of their respective formulation
2. History of congenital long QT syndrome or known history of prolonged QT interval OR Fridericia correction formula (QTcF) > 500 msec on electrocardiogram performed at screening.
3. Planned discharge within 24 hours of treatment initiation.
4. Subject is planning to conceive or father children within the projected duration of the study, starting with the screening visit through 120 days after the last dose of study treatment.
1. Ongoing usage of a Class IA or Class III antiarrhythmic agent (see Appendix D). At least 5 half-lives must elapse since any prior use of a Class IA or III antiarrhythmic agent prior to administration of study drug.

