All patients should commence assigned treatment as soon as possible and no later than 48 hours (2 calendar days) after randomization.

Stratification Factors

Patients will be stratified according to 3 factors:

- Age: <65 vs. ≥65
- History of hypertension prior to hospitalization: yes vs. no

- Influenza severity scale: 3 vs 4/5

Study site is not a stratification factor because the participating sites will be in close communication to minimize variability in providing BSC. Other potential factors that can influence clinical outcome include COPD, asthma, and cardiovascular disease will be assessed for their relationship to clinical outcome in exploratory analyses.

Blinding

This is a randomized, double-blind study. Patient treatment assignments will remain blinded. The study biostatisticians and clinical research pharmacist may access treatment assignment information as necessary.

The investigational drug blind will be maintained using the IWRS. The drug and placebo injections will be dispensed by the research pharmacy and packaged to be made indiscernible from one another. To maintain the blind, the IWRS will ensure the investigator or designee is unaware of the treatment arm assigned to the subject. Prior to dispensing the study medications, the research pharmacist will verify the appropriate treatment arm assignment using the IWRS cross-referencing the patient's randomization number. The study drug will be delivered to an unblinded administrator of the study drug who is not part of the study team and who will not disclose information regarding study drug administration to any member of the study team, the patient or anyone else.

Unblinding Procedure

The CSPCRPCC will not provide Emergency Code Envelopes to the Research Pharmacy for HITCH. Emergency unblinding will be managed through the 24-hour emergency call service [contact]). This number is also listed on the patient ID cards given to each patient participating in HITCH. The system managed by the CSPCRPCC will electronically capture up-to-date study drug assignment information gathered from the HITCH IWRS.

Authorization to Break the Blind

Under unusual circumstances, chiefly related to patient safety and emergency medical necessity, unblinding may be necessary if knowledge of the study treatment assignment will influence the medical treatment of the patient. This is usually done after consultation with the Study Chair.

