8. ADVERSE EVENTS AND SERIOUS ADVERSE EVENTS

Overview of Adverse Event Reporting

Timely and complete reporting of safety information assists study management in identifying any untoward medical occurrence. This contributes to patient safety, regulatory compliance and improvements in study design or procedures. In addition, close attention to AEs provides valuable information about the safety and tolerability of study drugs. This study specific safety plan is designed to collect information on the safety and tolerability of the study medications; thus, reporting will be conducted in accordance with the requirements of GCP and other regulatory requirements governing clinical research in the US.

Definitions and recording requirements for this trial are based on the International Conference on Harmonisation Efficacy Guideline 2a: Pharmacovigilance: Clinical Safety Data Management: Definitions and Standards for Expedited Reporting (ICH-E2A), the Code of Federal Regulations (21 CFR 312.32) and CSP Global Standard Operation Procedure (SOP) 3.6.

In HITCH, patients will receive a regimen of FDA approved commercially available degarelix for injection (Firmagon[®]) 240 mg for subcutaneous use or matching placebo. Local Study Investigators, with assistance from their local SC, are responsible for collecting AE and SAE information regarding the patients at their sites.

Non-serious AEs and SAEs will be collected from the time of randomization until 60 days after the last dose of study medication. Throughout the specified duration of AE and SAE collection, data will be collected through spontaneous local SC/LSI/Co-I contact, during in-person study visits, and gathered during telephone contacts and medical record reviews when performed (**see Table of Scheduled Events**). AEs will be collected based on a review of the electronic medical record. If a patient receives care at a non-VA facility for an AE or SAE, study staff should obtain the requisite release of information form(s) from the patient and acquire the pertinent medical records from the facility.

Adverse events that are open will require follow-up reports (if necessary) every 30 days until resolved or until the end of the trial.

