#### 3.8.1 AE and SAE analyses

Adverse events (AE) and serious adverse events (SAEs) are defined by the ICH for Clinical Safety Data Management (ICH-E2A), the Food and Drug administration as described in the section 9. Incidence of AE/SAEs will be summarized for each treatment group by body system and MedDRA term. The number and percentage of participants with each body system and MedDRA term will be presented for each group. Pearson  $\chi^2$  test and/or Fisher Exact test were used to compare the frequency difference of AE and SAE between the treatment groups in System of Body (SOC) and Preferred Terms (PT) levels. Tables to summarize the incidence rates will be created for each of the following groups: Total AE and SAE, AE and SAE by relationship to study treatment, AE and SAE leading to premature discontinuation, AE and SAE presented in descending order of frequency by MedDRA term (no body systems shown). AE and SAE that led to premature discontinuation from the study will be listed. These listings will contain details about the SAEs such as outcome and relationship to study treatments. Other supportive data, such as the participant's age, will be given. All AE and SAE will be coded with MedDRA (updated version) and listed by participant. Tables to summarize the incidence rates will be created for each of the following groups:

- AE and SAE (Table 3.8.1a-b)
- AE and SAE by relationship to study treatment (Tables 3.8.2a-b)

- AE and SAE leading to premature discontinuation (Table 3.8.3a-b)
- AE and SAE presented in descending order of frequency by MedDRA term (no body systems shown) (Table 3.8.4a-b)

AE and SAE that led to premature discontinuation from the study will be listed.

These listings will contain details about the AE/SAEs such as outcome and relationship to study treatment. Other supportive data, such as the participant's age, will be given. All AE/SAEs will be coded with MedDRA (updated version) and listed by subject (Table 3.8.5).

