## Appendix 5.2 Study Flow

### Appendix 5.3.1 Data Collection Schema

### Appendix 5.3.2 Data Collection Schedule

Form #	Form Name	Visit 00 (Screening / Baseline)	Visit 01 (Randomization / Day 1)	Visit 01 (Assessments 02-07)	Visit 02 (Day 8)	Visit 02 (Assessments 02-07)	Visit 03 (Day 15)	Visit 03 (Assessments 02-07)	Visit 04 (Day 22)	Visit 04 (Assessments 02-07)	Visit 05 (Day 30)	Visit 06 (Day 37)	Visit 07 (Day 44)	Visit 08 (Day 51)	Visit 09 (Day 60)	Visit 10-17 (if patient is still hospitalized complete weekly until discharge)
1	Screening and Randomization	R														
2	Demographics	R														
3	Medical History	R														
4	Baseline Medical Status	R														
5	Study Treatment		R													
6	Concomitant Medication Log	A	A	A	A	A	A	A	A	A	A	A	A	A	A	A
7	Medical Status				R		RH		RH		RH	RH	RH	RH	RH	RH
8	Laboratory Measures	R	R		R		RH		RH		RH					
9	Ordinal Scale of Clinical Status**	R	R	A	R	A	RH	A	RH	A	RH	RH	RH	RH	RH	RH
10	Protocol Deviation	A	A	A	A	A	A	A	A	A	A	A	A	A	A	A
11	Adverse Event	A	A	A	A	A	A	A	A	A	A	A	A	A	A	A
12	AE Follow-up	A	A	A	A	A	A	A	A	A	A	A	A	A	A	A
13	Serious Adverse Event	A	A	A	A	A	A	A	A	A	A	A	A	A	A	A
14	SAE Follow-up	A	A	A	A	A	A	A	A	A	A	A	A	A	A	A
15	Participant Termination		A	A	A	A	A	A	A	A	A	A	A	A	A	A
16	Research Blood and Nasal Swab Collection (GLA)										RH					
17	Total Testosterone Measurement (CSP completion)										R					
18	Post Discharge Follow-up										RD				RD	

R = Required

RH=Required if patient is still hospitalized (i.e. until discharge is noted on Form 07).

RD=Required if patient was discharged

A = As needed

\*\*Ordinal Scale of Clinical Status will be completed at screening, day 1 and whenever a status change occurs in the patient, but no less than 1x week.

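### Safety comparisons of SAEs and special-interest events count from randomisation with no onset-after-injection condition, so pre-injection events enter both arms; the dilution is small and removable at almost no cost

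*SAP*

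**What the plan says.** **Start of collection.** Both documents open the window at randomisation, although they close it at different times. SAP 2.5.3: "Non-serious AEs and SAEs will be collected from the time of randomization", with the window closing 30 days after the dose. Protocol section 8: "Non-serious AEs and SAEs will be collected from the time of randomization until 60 days after the last dose of study medication".

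**Time of injection.** SAP 2.3: "Study drug treatment will be given according to the randomization assignment within 48 hours after randomization". Protocol section 4 agrees: "All patients should commence assigned treatment as soon as possible and no later than 48 hours (2 calendar days) after randomization". The protocol synopsis (Study Treatments) differs: "The degarelix or matched placebo will be administered within 24 hours of randomization". The two drug-supply subsections of Protocol section 6 also give 24 hours. Protocol section 6 (Description of Treatment Regimens) says day 1, and SAP 2.3 itself later places the dose on the day of randomisation. These passages must be reconciled.

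**What is recorded.** Under SAP 2.5.3 and Protocol section 8, an AE goes on a form if it is judged related to study drug; every SAE is recorded regardless of cause. Any grade 3–5 arrhythmia or thromboembolic event is reported like an SAE, with no relatedness condition.

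**What is compared.** The safety population is everyone randomised (SAP 3.3), and all safety analyses use it (SAP 3.8). SAP 3.8.1 uses Pearson or Fisher tests to "compare the frequency difference of AE and SAE between the treatment groups". SAP 3.8.2 tests the special-interest events once they reach 25%; a significant excess on degarelix at alpha 0.01 goes to the DMC for a recommendation on termination. Neither section, nor the AE analysis text in Protocol section 10, defines a treatment-emergent event or sets an onset condition.

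**The concern.** The SAP elsewhere treats the injection as the start of treatment. Baseline is the last value before treatment (SAP 3.1.2), and medications are split into prior and concomitant at drug administration (SAP 3.6). The hours between randomisation and injection are thus pre-treatment for baseline and medications, but outcome time for safety.

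An SAE or arrhythmia in those hours cannot be due to degarelix. It still counts as an event of the patient's arm in the all-SAE tables and in the test that may lead to a termination recommendation. Adding the same background risk to both arms moves a risk ratio toward 1 and costs power in a comparison of only 132 and 66 men. Restricting the safety population to men who were injected would not remove these events, because the problem is when the event occurred, not who was dosed.

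**Working it through.** The documents give no event rate, event timing or power figure for the safety comparison, so there is no stated figure to reproduce. What follows is a range on stated assumptions.

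**Inputs from the documents.** Arm sizes are 132 and 66 (SAP 2.3). The gap is up to 48 hours or 24 hours, depending on the passage. The window is 30 days (SAP) or 60 days (protocol) after the dose. Alpha is 0.01 (SAP 3.8.2), taken as two-sided from the general convention in SAP 3.1.2.

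**Assumed inputs.** Post-injection risks are 15% on placebo and 30% on degarelix (ratio 2.0). The pre-injection risk q is the same in both arms, with a daily hazard 1 to 5 times the placebo post-injection hazard.

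**Step 1: quick check on the ratio.** With constant risk, the share of placebo-rate events falling before injection is f = gap/window. The observed ratio is f + 2(1 − f) = 2 − f.
- 60 days: f = 2/60 = 3.3%, ratio 1.97.
- 30 days: f = 2/30 = 6.7%, ratio 1.93. If the gap is added to the window, f = 2/32 = 6.25% and the ratio is 1.94.

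**Step 2: risks and power.** Observed risk = 1 − (1 − q)(1 − p), so the observed risk difference is (1 − q) times the true one. For constant hazard, a 48-hour gap and 30 days:
- Daily hazard = −ln(0.85)/30 = 0.00542; q = 1 − exp(−2 × 0.00542) = 1.1%, or about 2 of 198 men.
- Placebo: 1 − 0.9892 × 0.85 = 15.9%. Degarelix: 1 − 0.9892 × 0.70 = 30.8%.
- Ratio 1.93; difference 14.8 points.

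Power uses the normal approximation for two proportions, with pooled variance under the null and unpooled under the alternative.

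| Scenario (15% vs 30%) | q | Risk ratio | Difference, points | Power at 0.01 |
|---|---|---|---|---|
| Onset at or after injection only | 0 | 2.00 | 15.0 | 38.0% |
| 48 h, 60 days, constant hazard | 0.5% | 1.97 | 14.9 | 37.0% |
| 48 h, 30 days, constant hazard | 1.1% | 1.93 | 14.8 | 36.1% |
| 48 h, 30 days, early hazard ×5 | 5.3% | 1.73 | 14.2 | 29.7% |

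A 24-hour gap with 30 days gives the same values as 48 hours with 60 days.

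**Step 3: wider range.** Over gaps of 24 or 48 hours, windows of 30 or 60 days, early hazard ×1 to ×5 and assumed risks of 10/20%, 15/30% and 25/45%, q runs from 0.2% to 9.1% and the power loss from 0.2 to 12.6 points. If event times instead decay exponentially, f = (1 − exp(−g/τ))/(1 − exp(−60/τ)) for a gap of g days and mean τ. With g of 1 to 2 days, τ = 14 gives ratios of 1.93 to 1.87 and τ = 7 gives 1.87 to 1.75. These means are illustrative.

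**The case against.** The strongest reply is that the plan already filters most of this. Both related categories in SAP 2.5.3 require a plausible time sequence from administration, so a non-serious event before injection should be judged unrelated and not recorded. SAP 3.8.1 also tabulates events by relationship, where pre-injection SAEs should appear as not related. This stands. A reader might infer that every AE comparison is diluted, and the documents do not support that. The all-SAE tables and the special-interest test remain exposed, because neither applies a relatedness condition.

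Three other inferences are tempting.

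- **That screening events are analysed.** SAP Appendix 5.3.2 marks the AE and SAE forms as needed at Visit 00, and Protocol Table 1 marks AEs at screening. An available form does not show that its entries reach a between-arm comparison, and the text of both documents starts collection at randomisation. The schedule and text conflict; no more than that is established.
- **That the rule favours degarelix.** Before injection neither arm is exposed, so these events are balanced in expectation and the absolute difference hardly changes.
- **That the toxicity safeguard is weaker throughout.** Extra early events bring the 25% trigger sooner. It is the test that follows that loses power.

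The 48-hour gap is also a maximum. Other passages give a shorter one, and Protocol section 4 asks for treatment as soon as possible.

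**Conclusion.** The point holds for SAEs and for grade 3–5 arrhythmia and thromboembolic events. They count from randomisation, and nothing limits their comparison to onset after injection. Under constant risk the effect is small: a true ratio of 2.0 appears as about 1.93 to 1.97 even if every man waits the full 48 hours, and the toxicity test loses about 1 to 2 points of power in the 15% vs 30% case. It is moderate only if early clustering is assumed, for example a ratio of 1.73 and a loss of about 8 points with a fivefold early hazard. Event rates and timing are assumptions throughout. The reason to act is that the correction is nearly free and makes the comparison that can end the trial for harm cleaner. It is not that the present rule is likely to hide a large effect.

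**What to change.** - In SAP 3.8.1 and 3.8.2, base the between-arm SAE and special-interest comparisons, including the alpha 0.01 toxicity test, on events with onset or worsening at or after the study injection. Give a rule for events dated on the day of injection when the time is unknown.
- List events between randomisation and injection separately by arm, and keep collection from randomisation as it is, so that no information is lost.
- Say how randomised men who are never injected are handled in these comparisons.
- Reconcile the 48-hour, 24-hour and day-1 passages on the time of injection, and the AE/SAE entries at screening (Protocol Table 1, SAP Appendix 5.3.2) with the stated start at randomisation.

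The cost is SAP wording and one derived flag. SAP 2.5.3 lists onset date among the AE items, and a Study Treatment form is required at Visit 01. The forms themselves are not in the documents, so it should be confirmed that the SAE form holds the onset date and the treatment form the injection date. If they do, no new data are needed.
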